14.3.4.2.1. Phase 3 Primary Endpoint Analysis

The primary PFS analysis will be performed on the ITT population for Phase 3 patients in and on the PP population as a supportive analysis. The stratified log-rank test will be used to test the null hypothesis that the PFS distributions are the same for both treatment groups versus the alternative hypothesis that the duration of PFS for the selinexor arm is longer than the placebo arm using a 1-sided test and alpha=0.025 level of significance, adjusted using the CHW method.

Multivariable Cox proportional hazards model will be used to assess PFS, adjusted for stratification factor and other prognostic covariates. Model assumptions will be examined, and in the presence of non-proportional predictors, stratification or including a time-dependent variable of the non-proportional predictors will be considered as appropriate.

14.3.4.2.2. Phase 3 Secondary Key and Efficacy Endpoint Analysis

Secondary Key Endpoint Analysis

Key secondary variables will include the following, assessed in hierarchical fashion in the order presented (to preserve the overall Type I error for the study), according to the definitions described in the objectives and study endpoints:

- OS for non-inferiority
- OS for superiority

OS endpoints will be analyzed using the stratified log-rank test as described above. In sensitivity analysis for OS, the 2-stage estimation method will be implemented to assess the impact of cross-over on the effect of selinexor on OS ([Latimer 2017](#), [Latimer 2018](#)).

Secondary Efficacy Endpoint Analysis

The comparison of TTP in the current study to TTP on the most recent prior therapy will be performed as time-to-event using a stratified log-rank test stratified by patient IDs to account for correlation within patient and adjusted for treatment arm. Note that TTP for the current study may represent censored results, therefore, to minimize the impact of censoring, this analysis may require maturation of the TTP data beyond the required time at which the number of events for the primary PFS analysis at the end of Phase 3 have occurred.

Comparison of ORR between the two treatment arms will be performed using the Cochran-Mantel-Haenszel (CMH) χ^2 or exact test as appropriate, stratified by the randomization stratification factors. For OS, an additional descriptive comparison of the median OS from the randomized selinexor arm will be made to historical OS to the extent feasible, to assist in providing the proper context for the ITT analysis of selinexor versus placebo.

[figure not shown]
DOT and PFS according to the Investigator will be analyzed using the stratified log rank test as described above.

QoL Analysis

[figure not shown]
The QoL endpoint as assessed by the EORTC QLQ-C30 and EuroQoL EQ-5D-5L questionnaires will be analyzed as a total score, using a linear mixed effects model with fixed effect of treatment arm, randomization stratification factors, and the baseline value for the parameter in the model as a covariate, as well as random effect of subjects and repeated measures over time points. For EORTC QLQ-C30 the transformed score will be used, calculated according to the *EORTC QLQ-C30 Scoring Manual*. For the EuroQoL EQ-5D-5L questionnaire, the overall health score will be used.

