| 
Study Population: This study will enroll patients \geq 12 years of age with DDLS per World Health Organization (WHO) Response Criteria (Miller 1981) for Phase 2 and per RECIST v. 1.1 (Eisenhauer 2009) for Phase 3 who have received at least 2 but no more than 5 prior systemic therapies for the treatment of liposarcoma who meet all of the inclusion criteria and none of the exclusion criteria.
 | | |
| 
Study Treatment, Dose, and Mode of Administration: Blinded Study Treatment (Phases 2 and 3): Selinexor at a fixed oral dose of 60 mg or matching placebo will be given twice weekly during Weeks 1-6 of each 6-week (42-day) cycle until PD per RECIST v. 1.1, intolerance, consent withdrawal, or unblinding.
 | | |
| 
Open-label Selinexor: Patients on open-label selinexor will receive selinexor 60 mg twice-weekly during Weeks 1-6 of each six-week (42-day) cycle until PD, intolerance, or consent withdrawal.
 | | |
| 
Duration of Treatment and Follow-up: Following a 21-day screening period, patients may receive study treatment until they meet the criteria for discontinuation of study treatment or withdraw from the study. Patients will be followed for survival until the end of the study, withdrawal criteria are met, or death.
 | | |
| 
Statistical Methods: Based on the planned analysis of PFS by WHO and RECIST v. 1.1 Criteria in the Phase 2 portion of the study, the response criteria for the primary analysis (PFS) were changed from WHO to RECIST v. 1.1 in Version 4.0 of the protocol. Consequently, data from the Phase 2 portion of the study will be excluded from the final efficacy analysis in order to maintain statistical integrity and preserve overall Type I error rate. (Phase 2 safety data will be integrated with the Phase 3 safety data in the final safety analysis.)
 | | |
| 
Phase 2: All Phase 2 analyses will be conducted among Phase 2 patients only.
 | | |
| 
Phase 2 Primary Endpoint Analysis: The primary endpoint PFS for Phase 2 is defined as the time from date of randomization until the first date of PD, per RECIST v. 1.1, or death due to any cause. A preplanned preliminary analysis of PFS after 40 PFS events was conducted with an 11 August 2017 data cut with 49 eligible patients whose treatment assignments were available. Patients were analyzed in the treatment arm to which they were randomized. The preliminary PFS
 | | |

| Sponsor: | Investigational Product: | Developmental Phase: |

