|---|--------------------------|----------------------|
| Karyopharm Therapeutics Inc. | Selinexor (KPT-330) | Phase 2-3 |
| 
analysis was conducted by both WHO and RECIST v. 1.1 Criteria and served as a guideline to inform the final design of the Phase 3 portion of the study.
 
At the time of the preliminary PFS analysis, there were 48 events by WHO (22 selinexor, 26 placebo) and 28 events by RECIST v.1.1. (10 selinexor, 18 placebo). Both analyses showed trends favoring selinexor over placebo, while RECIST v. 1.1 results show a more significant effect size (hazard ratio [HR] of 0.84, 95% CI [0.47, 1.49] by WHO as compared with HR of 0.60, 95% CI [0.28, 1.31] by RECIST v. 1.1). A Landmark analysis based on RECIST v. 1.1 for patients continuing on study after 45 days showed a more significant HR of 0.24 (95% CI [0.05, 1.15]) in favor of selinexor.
 
Of the 57 patients in Phase 2, 56 met the eligibility criteria for the study. The formal primary Phase 2 PFS analysis will be performed on all 56 eligible patients randomized to study treatment in Phase 2 when their treatment assignments are unblinded. Phase 2 patients will be analyzed in the treatment arm to which they are randomized.
 
Phase 3:
 
The final efficacy analysis will be conducted among Phase 3 patients only.
 
Phase 3 Primary Endpoint Analysis
 
The primary PFS analysis will be performed on the intent-to-treat (ITT) population for Phase 3 patients and on the per-protocol (PP) population as a supportive analysis. The stratified log-rank test will be used to test the null hypothesis that the PFS distributions are the same for both treatment groups versus the alternative hypothesis that the duration of PFS for the selinexor arm is longer than the placebo arm using a 1-sided test and alpha=0.025 level of significance, adjusted using the Cui, Hung, and Wang (CHW) method (Cui 1999).
 
Phase 3 Sample Size and Statistical Power
 
Per protocol, the Phase 3 sample size was re-evaluated based on the Phase 2 results. Sample size calculations were conducted under the following assumptions:
 
CCI
 
Based on these assumptions, approximately 277 eligible patients will be randomized to receive either selinexor (60 mg twice weekly) or placebo in a blinded manner to observe 209 PFS events.
 
CCI
 | | |
| [REDACTED] | | |

Table 1: Schedule of Assessments and Study Activities: Blinded Phase 2 and Phase 3

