7. STUDY DESIGN

7.1. Study Design Overview

This is a Phase 2-3, multicenter, randomized, double-blind, placebo-controlled study of patients diagnosed with advanced, unresectable liposarcoma. Approximately 334 total patients will be randomized to study treatment (selinexor or placebo) as described below.

Patients must provide written informed consent AND meet all the inclusion criteria and have none of the exclusion criteria, before any screening tests not routinely performed may be conducted. The study flow chart is shown in [Figure 1](#) and the disposition of patients is shown in [Figure 2](#) and [Figure 3](#).

Phase 2:

- Fifty-seven patients were randomized to selinexor (60 mg) or placebo in a 1:1 allocation.
- Randomization was stratified based on the following stratification factors for patients enrolled under protocol Versions ≤ 4 : number of prior systemic therapies (1 versus ≥ 2) and prior eribulin use (prior eribulin versus no prior eribulin).

The preplanned analysis of PFS was performed and served as a guideline to inform the final design of the Phase 3 portion of the study. See Section [4.3.2](#) for the preliminary efficacy results for Phase 2.

Phase 3:

- Approximately 277 patients will be randomized to selinexor (60 mg) or placebo in a 2:1 allocation (~185 selinexor, ~92 placebo).
- Randomization will be stratified based on (a) prior eribulin use (prior eribulin versus no prior eribulin), (b) prior trabectedin (Yondelis[®]) use (prior trabectedin versus no prior trabectedin), and (c) the number of prior systemic therapies excluding eribulin and trabectedin (2 versus ≥ 3).

An interim analysis was conducted at 108 PFS events (see Section [14.1.1.2.1](#)).

The Schedule of Assessments for Blinded Phase 2/Phase 3 Treatment and Open-label Selinexor are provided in [Table 1](#) and [Table 2](#), respectively.

Study treatment (selinexor or matching placebo) will be given twice weekly on Day 1 and Day 3 during Weeks 1-6 of each six-week (42-day) cycle, without interruption between cycles.

All radiographic responses will be determined by the central reader (see the *Imaging Manual* for more details).

PD per RECIST v. 1.1. will be determined by the central reader. Details for continuation of study treatment following PD and the primary PFS analysis and follow-up after discontinuation of study treatment are provided in Section [7.2](#).

Treatment will continue until one or more of the following occurs:

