- Assessment of progression/extent of liposarcoma by RECIST v. 1.1 (2) when tumor (CT/MRI) scans are performed. Assessments are to be performed approximately 12, 18 and 24 weeks after start of study treatment (ie, Day 1 of Cycles 3, 4 and 5), and approximately every 12 weeks thereafter (ie, Day 1 of odd-numbered- Cycles ≥ 7), based on tumor scans.
- Treatment assignment query of patients and Investigators (only for patients with PD; query after PD but prior to unblinding) (Section 10.7.2).
- QoL questionnaires (EORTC QLQ-C30 and EuroQoL EQ-5D-5L) (Day 1 only, predose) (Section 10.7.1)
- Study treatment: in clinic dosing and dispensing of for home use (Days 1 and 22)
- AEs and SAEs (throughout the cycles)
- Concomitant medications (throughout the cycles)

9.1.5.1. Phone Calls with Patient: Cycles ≥ 3 Days 10, 17, 31 and 38 (+ 1 day)

A phone call will be made to the patient to evaluate supportive care medications, concomitant medications, and AEs/SAEs, and to adjust supportive care as appropriate.

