14.3.7. Procedures for Handling Missing Data

No imputation of missing efficacy data is planned for the primary analysis of efficacy endpoints. For patient reported QoL measurements, missing data will be handled as described in the *EORTC-QLQ-C30* and *EuroQoL EQ-5D-5L Scoring Manuals*. Additional sensitivity analyses will be done using the Jump to Reference (J2R) and last observation carried forward imputation approaches.

For time to event analyses, patients who have no efficacy evaluations will be considered as censored at time 0. For OS, patients will be censored on the date they were last known to be alive regardless of disease status.

For AEs, missing dates will not be imputed; however, if partial dates are available, they will be used to assess if the AE occurred during the treatment period. Missing severities of AEs will not be imputed and will be considered missing in any tabulations of AE severity. If an AE is missing a response to the question regarding relationship to treatment, the event will be considered to be related.

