4.2.2.2. QLQ-C30

QLQ-C30 contains 30 questions and includes five functional scales (Physical, Role, Emotional, Social, and Cognitive Functioning), three symptom scales (Fatigue, Nausea/Vomiting and Pain) and a Global Health Status/QoL scale, and six single-item symptom items (dyspnoea, insomnia, appetite loss, constipation, diarrhoea and financial difficulties). The principle for scoring these scales is the same: 1. Calculate the mean of the items that contribute to the scale; this is the raw score. 2. Use a linear transformation to standardise the raw score, so that scores range from 0 to 100.

For functional scales and the global health status/QoL, a higher score represents a better level of functioning (better health status); for symptom scales/items, a higher score represents a higher level of symptomatology/problems (worse health status).

The missing data will be handled based on EORTC QLQ-C30 scoring manual (Fayers et al., 2001). The raw score (mean of the items that contribute to the scale) will only be calculated if at least half of the items (i.e., 3 of 6 items, or 3 of 5 items) from the domain have been answered. As a result, none of the single-item measures will be imputed.

The actual value and change from baseline before initiating a new antineoplastic treatment will be summarized using descriptive statistics over time for each of the five functional scales, three symptom scales and six items, and the global health status/QoL scale.

QLQ-C30 analyses will be summarized by treatment arm among Ph3-ITT, Ph3-PP, and Ph2-ITT populations. For exploratory purpose, QLQ-C30 will also be summarized in Ph3-OL and Ph2-OL populations, in which changes from baseline will be calculated using baseline values for the open-label period, i.e., last assessment on or before the start of open-label treatment.

Table 4-2 Scoring the QLQ-C30 version 3.0

	Scale	Number of items	Item range*	Version 3.0 Item numbers	Function scales
Global health status / QoL					
Global health status/QoL (revised) [†]	QL2	2	6	29, 30	
Functional scales					
Physical functioning (revised) [†]	PF2	5	3	1 to 5	F
Role functioning (revised) [†]	RF2	2	3	6, 7	F
Emotional functioning	EF	4	3	21 to 24	F
Cognitive functioning	CF	2	3	20, 25	F
Social functioning	SF	2	3	26, 27	F
Symptom scales / items					
Fatigue	FA	3	3	10, 12, 18	
Nausea and vomiting	NV	2	3	14, 15	
Pain	PA	2	3	9, 19	
Dyspnoea	DY	1	3	8	
Insomnia	SL	1	3	11	
Appetite loss	AP	1	3	13	
Constipation	CO	1	3	16	
Diarrhoea	DI	1	3	17	

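### The protocol's QoL mixed model lists no fixed effect for visit, so if it is run, a QoL trend that continues over visits leaks into the arm contrast when the arms contribute different numbers of visits

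*Protocol*

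**What the plan says.** Protocol 14.3.4.2.2 (QoL Analysis) gives the fixed part of the model as "fixed effect of treatment arm, randomization stratification factors, and the baseline value for the parameter in the model as a covariate", and completes the sentence with "as well as random effect of subjects and repeated measures over time points". That closing clause is the only mention of time.

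During blinded treatment the questionnaires are given at screening, then once per 6-week cycle ("QoL questionnaires (EORTC QLQ-C30 and EuroQoL EQ-5D-5L) (Day 1 only, predose", Protocol 9.1.4 and 9.1.5), and at the End of Blinded Treatment visit (9.1.6). Blinded treatment runs "until PD per RECIST v. 1.1, intolerance, consent withdrawal, or unblinding" (Synopsis), so the number of QoL records per patient follows time on treatment. Questionnaires continue in open-label treatment (9.2.1 to 9.2.4), and 14.3.4.2.2 does not say whether those records enter the model.

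For missing QoL data, Protocol 14.3.7 adds: "Additional sensitivity analyses will be done using the Jump to Reference (J2R) and last observation carried forward imputation approaches".

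SAP 4.2.2.2 has no mixed model for QLQ-C30: "The actual value and change from baseline before initiating a new antineoplastic treatment will be summarized using descriptive statistics over time". SAP 4.2.2.3 does the same for EQ-5D-5L. SAP 1.7, which lists departures from the protocol's statistics, does not mention the QoL model. Part of that list is redacted, but its opening sentence says the dropped endpoints are all exploratory apart from one Phase 2 secondary. QoL is a Phase 3 secondary objective, so the redacted lines should not concern it.

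**The concern.** Read as written, the mean model has no term for visit and none for arm-by-visit. The arm coefficient is then a difference averaged over whatever visits each arm happens to supply. A trial designed to show longer PFS expects the arms to differ in time on treatment, and so in how many late-cycle questionnaires they return. If scores drift over time for reasons common to both arms, the arm with more late records has a different average for that reason alone. A subject random intercept absorbs differences in level between patients, not a trend within patients.

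This is the only inferential QoL analysis in either document. If it is run as stated, its estimate mixes any effect on QoL with the effect on time on treatment.

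**Working it through.** **No figure to reproduce.** The documents give no QoL power, SD, effect size or trajectory, and the PFS assumptions behind 209 events are redacted.

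**Inputs from the documents.** Allocation: "Approximately 277 patients will be randomized to selinexor (60 mg) or placebo in a 2:1 allocation (~185 selinexor, ~92 placebo" (Protocol 7.1). SAP 1.1 reports 285 randomized in Phase 3, which is 190 and 95 at 2:1. Visits are 6-weekly. The illustrative ratio for time on treatment is the Phase 2 PFS result, "HR of 0.60, 95% CI [0.28, 1.31] by RECIST v. 1.1" (Synopsis). It rests on 28 events and is a PFS ratio, not a ratio of treatment durations.

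**Assumed inputs.** Exponential time on treatment, placebo median 2 or 3 months (or 12 weeks), between-patient SD 15 and within-patient SD 12 on a 0-100 scale, no QoL difference between arms at any visit, dropout unrelated to QoL, and at most 8 or 12 visits. Stratification factors were left out.

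**Model as stated.** Y_ij = b0 + b1·arm_i + strata_i + b2·baseline_i + u_i + e_ij.

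**Approximation by hand.** With a shared fall of d points per visit, a patient with n visits has an average trend of −d(n+1)/2. Weighting patients equally, the spurious arm difference is −d × (mean visits selinexor − mean visits placebo)/2. With 3.61 and 2.57 visits and d = 3, this is −3 × 1.04/2 = −1.56 points. The mixed model gives more weight to patients with more visits, so simulated values tend to be somewhat larger.

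**Simulation without a visit term, duration HR 0.6.** Columns are the shared decline in points per cycle.

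| Setting | Quantity | 1 | 2 | 3 | 5 |
|---|---|---|---|---|---|
| 185/92, median 2 months, max 8 visits (about 3.6 v 2.6 visits) | bias by hand | −0.52 | −1.03 | −1.56 | −2.55 |
| | bias simulated | −0.64 | −1.04 | −1.64 | −2.87 |
| | false-positive rate | 5.8% | 10.1% | 18.9% | 43.6% |
| 185/92, median 3 months, max 8 visits (about 4.5 v 3.4) | bias simulated | −0.59 | −1.07 | −1.75 | −2.88 |
| | false-positive rate | 4.8% | 10.3% | 22.1% | 47.7% |
| 190/95, median 12 weeks, max 12 visits (4.9 v 3.4), REML | bias by hand | −0.75 | −1.50 | −2.25 | −3.75 |
| | bias simulated | −0.8 | −1.8 | −2.5 | −4.3 |
| | false-positive rate | 7.5% | 20.3% | 32.2% | 59.8% |
| 185/92, median 12 weeks, max 12 visits, variances fixed | false-positive rate | 10% | 20% | 40% | 74% |

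The first two settings also treat the variances as known, with 1000 runs each, as in the last row. The REML setting used 600 runs. A 60-run REML check of the first setting at 3 points gave −2.18 without visit and −0.42 with it, a gap of −1.76. The corresponding gap from the 1000-run simulation is −1.64 − 0.10 = −1.74.

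**What moves the result.**
- Duration HR 0.7 (median 2 months, max 8 visits): bias −0.3 to −2.0 points, false-positive rate 6.0% to 25.4% for declines of 1 to 5 points.
- Duration HR 0.8 (max 12 visits, REML): 7% to 15%.
- Equal duration: bias at most 0.05 point, rate 4.5% to 6.9%.
- Whole drop present by the first post-baseline visit: bias within 0.1 point, with or without a visit term.
- Decline levelling off after visit 2: 4% to 7%. After visit 3: 5% to 13%.
- Open-label records included, with an assumed 60% crossover: mean visits 4.2 (selinexor) v 4.9 (placebo), bias +0.3 to +1.5 points, rate 5% to 9%.

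**With a categorical visit term.** In the 1000-run settings at median 2 or 3 months the bias is −0.09 to +0.11 point and the rate 3.8% to 6.3%. Across all settings the rate is 3% to 8%, which is nominal within simulation error.

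**The case against.** The strongest reply is that the SAP is the operative plan and does not run this model. Summaries by time point are already conditional on visit, so this bias cannot arise in them. That stands, and it limits the point. It does not remove it: the protocol model is not withdrawn in the readable text, and someone following Protocol 14.3.4.2.2 would run it as written.

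Second, "as well as random effect of subjects and repeated measures over time points" may be loose shorthand that includes visit as a factor. The wording normally describes the correlation among repeated observations and does not put visit in the mean. If a visit factor was intended, one sentence settles it.

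Third, a reader might infer that any shared decline is charged to treatment once durations differ, or that the better selinexor does on PFS, the worse it must look on QoL. The documents support neither. The decline has to continue past the first post-baseline visit, and no QoL trajectory is given. The steady fall is severe if it lasts: 3 points over 12 cycles is 36 points. The direction also depends on a data cut that 14.3.4.2.2 does not state, since placebo patients who cross over go on completing questionnaires. Treatment also ends for toxicity, which could shorten selinexor follow-up.

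Fourth, J2R and LOCF analyses are planned. They are sensitivity analyses and leave the main model unchanged. LOCF carries an early score into later visits, so it does not supply the missing trend for patients who stop early.

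Finally, QoL lies outside the testing hierarchy, and SAP 4.2 advises caution with nominal secondary p-values. That lowers the stakes but does not make the estimate sound.

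**Conclusion.** The point holds in a conditional form. The protocol's listed fixed effects omit visit. If the model is run, visit numbers differ by arm and QoL keeps changing after the first post-baseline visit, the arm coefficient is biased. On blinded-phase records with longer selinexor treatment and a continuing decline, the bias is against selinexor. With crossover records included or earlier stopping for toxicity, it can favour selinexor.

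At a duration HR of 0.6 and a steady linear decline, the two-sided false-positive rate is about 5-10% at 1 point per cycle, 10-20% at 2 and roughly 20-40% at 3. The 5-point results vary too much between settings (44% to 74%) to be a headline. All these sizes depend on assumed SDs, durations, visit caps and trajectory. Informative dropout is a separate matter and was not simulated.

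The documents do not show that reported QoL results will be biased, because the SAP plans only descriptive summaries over time. What they show is an inferential model that is misspecified for unbalanced visits and has been neither carried forward nor withdrawn.

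**What to change.** In Protocol 14.3.4.2.2:
- Add categorical visit (6-week cycle) and arm-by-visit as fixed effects, keeping baseline and the stratification factors, and state the covariance structure.
- Define the treatment effect as the between-arm least-squares mean difference at a named visit, or as an equally weighted average over a fixed set of early visits.
- Restrict the model to blinded-phase records before new antineoplastic therapy, counting open-label selinexor as such for placebo patients. Say how selinexor-arm patients who continue open-label are cut, since SAP 2.4 counts their open-label time as blinded period.
- Assign End of Blinded Treatment questionnaires to the cycle window of their actual date.

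Then either carry this model into SAP 4.2.2.2 and 4.2.2.3, or list its removal in SAP 1.7 so that the descriptive summaries are clearly the whole QoL analysis.

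No new data are needed. The cost is a few degrees of freedom and the need to name the visit or visit set.
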